6.3. Exploratory Efficacy Endpoints

6.3.1. Definition of Exploratory Efficacy Endpoints

PPD

P
P
D

[Redacted]

[Redacted]

[Redacted]

6.3.2. Analysis Methods for Exploratory Efficacy Endpoints

PPD

[Redacted]

[Redacted]

[Redacted]

[Redacted]

[Redacted]

[Redacted]

6.4. Changes From Protocol-Specified Efficacy Analyses

There are no planned changes from protocol-specified efficacy analyses.

7. SAFETY ANALYSES

7.1. Safety Endpoints

The primary safety endpoint is any AE leading to permanent discontinuation of study drug(s).

7.2. Adverse Events and Deaths

7.2.1. Adverse Event Dictionary

Clinical and laboratory adverse events (AEs) will be coded using the current version of MedDRA. System organ class (SOC), high-level group term (HLGT), high-level term (HLT), preferred term (PT), and lower-level term (LLT) will be provided in the AE dataset.

7.2.2. Adverse Event Severity

Adverse events are graded by the investigator as Grade 1, 2, 3, or 4 according to toxicity criteria specified in the protocol. The severity grade of events for which the investigator did not record severity will be categorized as “missing” for tabular summaries and data listings and the most severe will be considered (for sorting purpose only) in data presentation.

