7.2.3. Relationship of Adverse Events to Study Drug

Related AEs are those for which the investigator selected “Related” on the AE case report form (CRF) to the question of “Related to Study Treatment.” Events for which the investigator did not record relationships to study drug will be considered related to study drug for summary purposes. However, by-subject data listings will show the relationship as missing from that captured on the CRF.

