7.2.5.2. Incomplete Dates

If the onset date of the AE is incomplete, then the month and year (or year alone if month is not recorded) of onset determine whether an AE is treatment emergent, as long as the AE stop date is not prior to the first dose date of study drug. The event is considered treatment emergent if both of the following 2 criteria are met:

- The AE onset and end dates are the same as or after the month and year (or year) of the first dose date of study drug
- The AE onset date is the same as or before the month and year (or year) of the 30th day after the date of the last dose of study drug

An AE with completely missing onset and stop dates, or with the onset date missing and a stop date later than the first dose date of study drug, will be considered to be treatment emergent.

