7.2.6. Summaries of Adverse Events and Deaths

A brief high-level summary of TEAEs will be provided by region and by the number and percentage of subjects who had the following: any AE; any AE of Grade 3 or above; any AE of Grade 2 or above; any treatment-related AE; any treatment-related AE of Grade 3 or above; any treatment-related AE of Grade 2 or above; any SAE; any treatment-related SAE; any AE that led to premature discontinuation of SOF/VEL, any AE that led to interruption of SOF/VEL. All deaths (including those that are treatment emergent and those that are not treatment emergent) observed during the study will also be summarized and included in this table.

Adverse event summaries will provide the number and percentage of subjects with TEAEs by SOC and PT, by region based on the Safety Analysis Set as follows:

- All AEs
- AEs of Grade 3 or above
- AEs of Grade 2 or above
- All treatment-related AEs
- Treatment-related AEs of Grade 3 or above
- Treatment-related AEs of Grade 2 or above
- All SAEs
- All treatment-related SAEs
- AEs leading to premature discontinuation of SOF/VEL

- Adverse Events Leading to Interruption of SOF/VEL
- Deaths

Multiple events will be counted only once per subject in each summary. Adverse events will be summarized and listed by region first in alphabetic order of SOC and then by PT in order of descending incidence within the Overall group within each SOC. In summaries by severity grade, the most severe grade will be used for those AEs that occurred more than once in an individual subject during the study.

In addition to the above summary tables, TEAEs will be summarized by PT only and by region, in order of descending incidence in the Overall group for:

- All AEs
- AEs that occurred in at least 5% of subjects within any region
- AEs of Grade 3 or above
- All treatment-related AEs
- All SAEs
- AEs leading to premature discontinuation of SOF/VEL
- AEs leading to interruption of SOF/VEL

In addition to the summaries described above, data listings by region and subject ID (in ascending order) will be provided for the following:

- All AEs
- AEs of Grade 3 or above
- SAEs
- Deaths
- AEs leading to premature discontinuation of SOF/VEL
- Adverse Events Leading to Interruption of SOF/VEL
- AE with changes other than resolution dates between the SVR12 and SVR24 analyses (provided only at the final analysis)

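### Adverse events with no recorded severity are left out of every Grade 2+ and Grade 3+ summary, whereas other missing AE attributes are resolved against the drug

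*SAP*

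**What the plan says.** **Missing severity (SAP 7.2.2).** "The severity grade of events for which the investigator did not record severity will be categorized as" 'missing', and this applies "for tabular summaries and data listings and the most severe will be considered (for sorting purpose only) in data presentation". No grade is assigned for counting.

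**Where grade is used (SAP 7.2.6).** The high-level summary includes rows for "any AE of Grade 3 or above; any AE of Grade 2 or above", and the same two thresholds for treatment-related events. The tables by system organ class and preferred term repeat all four thresholds, among them "Treatment-related AEs of Grade 3 or above". Grade 3+ events are also tabulated by preferred term alone. For repeated events, in summaries by grade, "the most severe grade will be used for those AEs that occurred more than once in an individual subject during the study". Nothing in 7.2.6 brings an ungraded event into a threshold count.

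**Other missing AE attributes.**
- Relationship (SAP 7.2.3): "Events for which the investigator did not record relationships to study drug will be considered related to study drug for summary purposes". The listings still show the relationship as missing.
- Dates (SAP 7.2.5.2): "An AE with completely missing onset and stop dates" is taken to be treatment emergent. So is an event with no onset date that stopped after the first dose.

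**The concern.** The plan has two conventions for missing AE information and gives no reason for the difference. When relationship or timing is unknown, the event is placed in the less favourable class in the summaries. When severity is unknown, the event is placed in no class that a grade-threshold summary counts.

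The two conventions meet in the treatment-related Grade 2+ and Grade 3+ summaries. An event with neither relationship nor severity recorded is counted as treatment-related but is absent from both related-and-graded counts.

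Safety and tolerability is a primary objective (SAP 1.1). The study gives one open-label regimen to all subjects (SAP 1.2), so absolute rates are read directly, with no concurrent arm subject to the same under-count. A rule whose only possible error is downward should at least be visible in the tables it affects.

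**Working it through.** The plan states no figure for this point, so there is nothing to reproduce. The check sets the rules side by side and then works out the effect per affected subject.

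**Step 1: the rules compared.**

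| Missing item | SAP section | Treatment in summaries | Direction |
|---|---|---|---|
| Relationship to study drug | 7.2.3 | Counted as related | Against the drug |
| Onset and stop dates both missing | 7.2.5.2 | Counted as treatment emergent | Against the drug |
| Baseline laboratory value (a parallel, not an AE attribute) | 7.3.2.1 | Any abnormality of Grade 1 or higher counted as treatment emergent | Against the drug |
| AE severity | 7.2.2 | Category 'missing'; most severe for sorting only | Not counted at any threshold |

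**Step 2: where an ungraded event goes.** It stays in the all-AE summaries and the all-AE listing. Where it qualifies, it also stays in the treatment-related, serious, discontinuation, interruption and death summaries. It is not counted in the four threshold rows of the high-level summary, the four threshold tables by system organ class and preferred term, or the Grade 3+ table by preferred term.

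**Step 3: effect per subject.** Let N be the number of subjects in the column and k the number whose only event at or above the threshold has no recorded grade. The reported percentage is then too low by 100 × k / N points. Planned sizes come from SAP 1.2.

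- Overall, N = 360, k = 1: 100 × 1/360 = 0.28 points
- Region 1, N = 260, k = 1: 100 × 1/260 = 0.38 points
- Region 2, N = 100, k = 1: 100 × 1/100 = 1.0 point
- Any column, k = 0: no effect

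**Step 4: illustration under assumptions.** The plan gives neither an expected Grade 3+ rate nor a rate of missing severity. Assume that 5.0% of subjects have a recorded Grade 3+ event, and that k further subjects have only an ungraded one that could qualify.

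| Column | Recorded Grade 3+ | Worst case, k = 1 | Worst case, k = 5 |
|---|---|---|---|
| Overall | 18/360 = 5.0% | 19/360 = 5.3% | 23/360 = 6.4% |
| Region 1 | 13/260 = 5.0% | 14/260 = 5.4% | 18/260 = 6.9% |
| Region 2 | 5/100 = 5.0% | 6/100 = 6.0% | 10/100 = 10.0% |

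The same formula applies to the Grade 2+ rows and to the treatment-related rows.

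**The case against.** The best defence is that the rule is explicit, prespecified and consistent with SAP 3.4.1, under which missing data are generally not imputed unless a method is given. Relationship and treatment emergence are yes/no attributes, so an event has to fall on one side. Severity has four levels, so a separate 'missing' category is a reasonable choice. Section 7.2.6 lists table topics and not layouts, so a 'missing' row could still be shown. Data are cleaned and queries resolved before analysis (SAP 2.2.2 and 2.3), and few or no grades may be missing at that point.

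Much of this stands. It argues against forcing a fixed grade, such as Grade 3, onto every ungraded event in the main tables. It does not remove the inconsistency: a threshold is itself a yes/no split, and the plan's rule always puts the ungraded event on the lower side. A possible 'missing' row is not specified, and would not change the threshold count if it were shown.

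Three stronger readings are tempting, and the SAP does not support them.

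- A reader might infer that, because 'missing' sorts as most severe, it could displace a recorded Grade 3 or 4 when the worst of several records is chosen. The restriction to sorting rules this out. A subject with any recorded Grade 3+ event belongs in the Grade 3+ count.
- A reader might infer that the plan assumes ungraded events were mild. It assigns no grade, and the events remain in the summaries listed in step 2 above.
- A reader might treat the Grade 3+ rate as the main safety result. The primary safety endpoint is an AE leading to permanent discontinuation of study drug (SAP 7.1), which does not use grade.

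**Conclusion.** The point holds as a minor inconsistency. Under 7.2.2 an ungraded AE is not counted in any Grade 2+ or Grade 3+ summary, all or treatment-related, while 7.2.3 and 7.2.5.2 resolve comparable gaps against the drug. The exclusion follows from the wording of 7.2.2 and from the absence of any overriding rule in 7.2.6; the SAP does not state it outright.

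The bias can only be downward: 0.28 points overall, 0.38 in Region 1 and 1.0 in Region 2 for each subject whose only Grade 3+ event is ungraded. These figures assume the planned column sizes. How many subjects are affected is unknown and may be none. A subject with another recorded Grade 3+ event is still counted in the any-AE row, so for that subject the loss is confined to the event or preferred-term level.

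**What to change.** Leave the listings as they are, showing severity as missing. Add to 7.2.2, with a cross-reference in 7.2.6, wording along these lines:

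> Each Grade 2+ and Grade 3+ summary, for all and for treatment-related TEAEs, will carry a row or footnote giving (a) the number of subjects with an ungraded TEAE who are not otherwise counted in that summary, and (b) the worst-case number and percentage of subjects when ungraded TEAEs are counted as meeting the threshold.

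For the treatment-related summaries, an event with no recorded relationship is handled as 7.2.3 already provides. The main count stays based on recorded grades, so no grade is imputed into it, and the worst-case figure follows the direction of 7.2.3.

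The cost is a short addition to the SAP and a small amount of programming. The downside is a possible slight overcount in the worst-case figure if an ungraded event was in fact below the threshold; that is visible because the recorded-grade figure stands beside it. If no grade is missing, the two figures coincide.

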7.2.3. Relationship of Adverse Events to Study Drug

Related AEs are those for which the investigator selected “Related” on the AE case report form (CRF) to the question of “Related to Study Treatment.” Events for which the investigator did not record relationships to study drug will be considered related to study drug for summary purposes. However, by-subject data listings will show the relationship as missing from that captured on the CRF.

7.2.4. Serious Adverse Events

Serious adverse events (SAEs) will be identified and captured as SAEs if AEs met the definitions of SAE specified in the study protocol. Serious adverse events captured and stored in the clinical database will be reconciled with the SAE database from the Gilead Drug Safety and Public Health Department before database finalization.

7.2.5. Treatment-Emergent Adverse Events

7.2.5.1. Definition of Treatment Emergent

Treatment-emergent adverse events (TEAEs) are defined as one or both of the following:

- Any AEs with an onset date on or after the study drug start date and no later than 30 days after permanent discontinuation of study drug.
- Any AEs leading to premature discontinuation of study drug.

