1.2. Study Design

This is an international, multicenter, open-label study that will evaluate the safety, tolerability and antiviral efficacy of SOF/VEL for 12 weeks in treatment-naïve and treatment-experienced adults with chronic HCV infection. Subjects with or without cirrhosis will be enrolled.

Approximately 20% of subjects may be treatment experienced and approximately 20% of subjects may have compensated cirrhosis at screening.

Subjects with chronic HCV infection will be enrolled to receive SOF/VEL once daily for 12 weeks.

This multi-regional clinical trial (MRCT) is planned to be conducted in China, Malaysia, Singapore, Thailand, and Vietnam. China will be considered Region 1. Malaysia, Singapore, Thailand, and Vietnam, which are all located in Southeast Asia, will be considered Region 2.

Approximately 360 subjects will be enrolled in the study in total. The approximate number of subjects to be enrolled in each region according to HCV genotype is represented in the table below:

HCV GT (Prior Rx History)	GT-1 (TN, TE)	GT-2 (TN, TE)	GT-3 (TN, TE)	GT-4,5,6 (TN, TE)	Total
Region 1 (China)	80	60	60	60	260
Region 2 (Malaysia, Singapore, Thailand, Vietnam)	100				100

Rx = Treatment
 TN = Treatment Naïve, TE = Treatment Experienced

It is expected that a small number of subjects whose HCV genotype cannot be determined by the central laboratory (HCV genotype indeterminate) may also be enrolled.

The schedule of assessments is provided as an appendix to the SAP ([Appendix 1](#)).

The total time to complete all study visits is up to approximately 42 weeks including the following periods:

- 42-day (6-week) screening period
- 12-week treatment period
- Up to 24-week posttreatment period

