7.3.2.1. Treatment-Emergent Laboratory Abnormalities

Treatment-emergent laboratory abnormalities are defined as values that increase at least 1 toxicity grade from baseline at any postbaseline time point, up to and including the date of last dose of study drug plus 30 days for subjects who permanently discontinued study drug, or all available data in the database snapshot for subjects who were still on treatment at the time of an interim analysis. If the relevant baseline laboratory value is missing, then any abnormality of at least Grade 1 will be considered treatment emergent.

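### SAP Section 7.2.5.1 has no worsening clause, so a pre-dose AE that worsens on SOF/VEL can drop out of the TEAE tables unless the worsening is recorded as a new event

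*SAP*

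**What the plan says.** Section 7.2.5.1 gives two routes to treatment emergence. The first is an onset window: "Any AEs with an onset date on or after the study drug start date". That window closes 30 days after SOF/VEL is stopped for good. The second route is "Any AEs leading to premature discontinuation of study drug", whatever the onset date.

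Section 7.2.5.2 adds rules for incomplete dates. With a partial onset date, month and year (or year alone) decide; one of the two conditions begins "The AE onset and end dates are the same as or after the month and year (or year) of the first dose date of study". An AE with both dates missing counts as treatment emergent, and so does one whose onset is unknown but which stopped after first dose.

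Section 7.2.6 builds its summaries on this definition: "Adverse event summaries will provide the number and percentage of subjects with TEAEs by SOC and PT". The high-level summary and the tables by preferred term alone are also summaries of TEAEs. The exception is deaths, all of which enter the high-level table whether treatment emergent or not. No treatment-emergence limit is stated for the by-subject listings, which cover all AEs, Grade 3 or above, SAEs, deaths, discontinuations and interruptions.

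For laboratory data, Section 7.3.2.1 uses a different idea: "values that increase at least 1 toxicity grade from baseline at any postbaseline time point".

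Pre-dose AE records can exist. Section 1.2 provides a "42-day (6-week) screening period", and the schedule in Appendix 1 marks AE collection at Screening and Day 1.

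**The concern.** An AE that begins at Grade 1 in screening, stays in the database as one record with its full onset date, and reaches Grade 3 or becomes serious on treatment meets neither route in Section 7.2.5.1. If it leads to interruption of SOF/VEL rather than discontinuation, it is still not admitted. It then appears in none of the TEAE tables for Grade 2 or above, Grade 3 or above, treatment-related events, SAEs or interruptions.

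Safety and tolerability is a primary objective (Section 1.1). The study is open-label and every subject receives SOF/VEL, so no comparator arm shares the omission. The effect runs one way: events can be left out by this route but never added.

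**Working it through.** The SAP states no figure that depends on this definition, so there is none to reproduce. The check applies the rule to cases and then gives an illustration of size.

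**Step 1: the rule.** Count first dose as Day 1 and take a last dose on Day 84 (12 weeks, Section 1.2). An AE with complete dates is a TEAE if its onset lies from Day 1 to Day 84 + 30 = Day 114, or if it led to discontinuation.

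| Case | Onset in window? | Led to discontinuation? | TEAE? |
|---|---|---|---|
| (a) Screening onset at Grade 1, Grade 3 on Day 30, one record | No | No | No |
| (b) Screening onset, non-serious, becomes serious on treatment, one record | No | No | No |
| (c) As (a) or (b), but leads to discontinuation | No | Yes | Yes |
| (d) Worsening entered as a new AE with onset Day 30 | Yes | No | Yes |

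Cases (a) and (d) are the same clinical course. Only the way of recording differs, and the SAP does not say which applies.

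**Step 2: what the second route implies.** An AE outside the onset window begins either before first dose or more than 30 days after permanent discontinuation. The latter cannot have caused that discontinuation. With complete dates, the second route therefore adds essentially only pre-dose AEs. The SAP thus expects some pre-dose records to keep their original onset date and later affect treatment. It brings back those that lead to discontinuation, but not those that worsen, become serious or lead to interruption.

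**Step 3: comparison with neighbouring rules.** An AE with a missing onset date and a stop date after first dose is counted. So is one with the onset day missing, in the month of first dose, if its end date is no earlier than that month. An AE with a known pre-dose onset and known on-treatment worsening is not. A laboratory value that rises one grade from baseline is counted under Section 7.3.2.1.

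**Step 4: size.** One event is 1/360 = 0.28% overall and 1/100 = 1.0% in Region 2. The SAP gives no rate for such events. Let q be an assumed share of subjects with an event of type (a) or (b). The expected number is Nq, and the chance of at least one is 1 − (1 − q)^N:

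| Assumed q | Expected, N = 360 | Chance of at least one, N = 360 | Expected, N = 100 | Chance of at least one, N = 100 |
|---|---|---|---|---|
| 0.2% | 0.7 | 51% | 0.2 | 18% |
| 0.5% | 1.8 | 84% | 0.5 | 39% |
| 1% | 3.6 | 97% | 1.0 | 63% |
| 2% | 7.2 | over 99% | 2.0 | 87% |

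The range of q is for illustration only.

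**The case against.** The strongest reply is that the exclusion depends on a convention not visible here. If a worsening is entered as a new AE, the first route captures it (case d). Such rules commonly sit in the protocol or the eCRF instructions, on which this SAP says it is based. That stands as a limit: the omission is conditional. It does not settle the matter, because the SAP states no such convention and its discontinuation route makes sense mainly if pre-dose records keep their onset date.

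A second reply is that the laboratory rule is no contradiction. Laboratory values are repeated measurements graded against a baseline, while AEs are reported records with an onset. That is fair. Where the deterioration is itself a graded laboratory value, Section 7.3.2.2 already tabulates it. The comparison shows only that the SAP accepts worsening as a basis for treatment emergence in one place and is silent in the other.

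Third, the number of affected records may be small. Medical history is collected separately at Screening, and the schedule does not say which pre-dose events are entered as AEs. This also stands, and no count can be derived from the SAP.

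A reader might infer more: that treatment emergence rests on onset date alone, that every worsened screening AE is lost from every table, or that such events go unreported. The SAP does not support this. Discontinuation is a separate route, Section 7.2.5.2 admits some incomplete dates, all deaths are tabulated, and the listings, including the one for interruptions, would show the case.

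**Conclusion.** The gap is real but conditional. It arises when an AE has a complete pre-dose onset date, the worsening stays on the same record, and the event does not lead to discontinuation. Such an event is then absent from the TEAE summary tables, including those for Grade 2 or above, Grade 3 or above, related events, SAEs and interruptions. It remains visible in the listings, but listings do not supply the tabulated rates.

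The primary safety endpoint (Section 7.1, AE leading to permanent discontinuation) and the all-deaths count are not affected, and no number in the SAP changes. The likely size is a few events at most, though this is a judgement because the SAP gives no rate. The reason to act is the direction of the omission and the low cost of closing it.

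**What to change.** Either of two changes to Section 7.2.5.1 is enough:

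- Add a third route: an AE that began before first dose and then rises in severity grade, or becomes serious, between first dose and 30 days after study drug is permanently stopped.
- Or state that any such worsening is recorded as a new AE with its own onset date, so that the first route captures it.

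If the first option is chosen and the date of worsening is unknown, list those cases separately. Counting every pre-dose Grade 3 or above or serious AE that merely continues past first dose would include events that never worsened on drug. A worsening clause also does not reach an interruption caused by a pre-dose AE whose grade and seriousness did not change. The SAP should say whether the interruption table is meant to include that case.

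The cost is one sentence and a small programming change before database finalization. TEAE counts may rise by a few events.
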